### 3 STUDY OBJECTIVES

#### 3.1 Primary Objective

The primary objective of this study is to:

- Evaluate the analgesic effect on average leg pain (as measured by the NPRS in the affected leg) following a single TF injection of SP-102 compared to an [REDACTED] injection of placebo over 4 weeks.

#### 3.2 Secondary Objectives

The secondary objectives of the study are to:

- Evaluate degree of disability over time as measured by the Oswestry Disability Index (ODI).
- Characterize the change of the subject's radiculopathy symptoms and overall condition using PainDETECT, Brief Pain Inventory-Short Form (BPI-SF), Clinical Global Impression of Change (CGIC), and Patient Global Impression of Change (PGIC).
- Evaluate the safety of a single and repeat SP-102 TF injection.

## 4 ENDPOINTS

### 4.1 Primary Efficacy Endpoint

The primary efficacy endpoint is the mean change from Baseline (D1) to Week 4 in the mean NPRS average pain score in the affected leg.

[REDACTED]

### 4.2 Secondary Efficacy Endpoints

The key secondary efficacy endpoint is:

- The change in ODI total score from Baseline (D1) to Week 4.

### 4.3 Other secondary endpoints

Other secondary endpoints are:

- PGIC at Week 2, Week 4, Week 8, and Week 12.
- The time to repeat injection of SP-102 from index injection.
- Proportion of subjects receiving repeat injection.
- The mean change from Baseline (D1) to Week 2, Week 4, Week 8, and Week 12 in the mean NPRS average pain score in the affected leg.
- The mean change from Baseline (D1) to Week 2, Week 4, Week 8, and Week 12 in the mean NPRS worst pain in the affected leg.
- The mean change from Baseline (D1) to Week 2, Week 4, Week 8, and Week 12 in the mean NPRS current pain score in the affected leg.
- The mean change from Baseline (D1) in the ODI total score to Week 12.
- The mean change in PainDETECT from Baseline (D1) to Week 4 and Week 12.
- The mean change in BPI-SF score from Baseline (D1) to Week 4 and Week 12.

- Proportion of subjects achieving a response of 30%, 50%, and 75% reductions from Baseline (D1) in mean NPRS average pain score in the affected leg at Week 2 and Week 4.
- The mean change from Baseline (D1) to Week 2, Week 4, Week 8, and Week 12 in the mean NPRS average pain score in the lower back.
- CGIC at Week 2, Week 4, Week 8, and Week 12.
- Cumulative use of rescue medication (mg of acetaminophen)
- Time to first rescue medication dose.
- Proportion of subjects requiring rescue medications.
- Percent of rescue medication free days.
- The mean change from Baseline (D1) to Week 4 in the mean morning (AM) NPRS average pain score in the affected leg.
- The mean change from Baseline (D1) to Week 4 in the mean evening (PM) NPRS average pain score in the affected leg.

#### 4.4 Safety Endpoints

- Adverse Events
- Change from Baseline (D1) in laboratory parameters
- Change from Baseline (D1) in vital signs
- Change from Baseline (D1) in neurological examination

### 5 SAMPLE SIZE

## 6 RANDOMIZATION

Using an Interactive Web Response System (IWRS), on D1, the site staff or research pharmacist will contact the IWRS after the Investigator has confirmed that the subject fulfills all the inclusion/exclusion criteria. The IWRS will assign a randomization number to the subject, which will be used to link the subject to a treatment arm. The research pharmacist will prepare the appropriate IP and deliver it to study staff in preparation for injection.

A randomization schedule will be employed to facilitate effective randomization and allocation concealment. The schedule will involve a block randomization technique, randomly assigning participants within blocks based on a 1:1 allocation ratio. The randomization schedule will be stratified by study site.

## 7 PLANNED ANALYSES

No statistical analysis plan (SAP) prepared in advance of the data can be absolutely definitive and the final clinical study report (CSR) may contain additional tables or statistical tests if warranted by the data obtained. The justification for any such additional analyses will be fully documented in the final CSR.

### 7.1 Analysis and Reporting Periods

Baseline, efficacy, and safety data will be summarized for the following analysis periods:

- Primary analysis period which includes data from baseline through 4 weeks of treatment
- Secondary analysis period which includes data from baseline to end of study (Week 24)

Also, there are two reporting periods in this study in which for each reporting period, data are summarized for both the primary and secondary analysis periods. These reporting periods are as follows:

- Primary analysis:

This is the final inferential analysis of all efficacy endpoints, along with analysis of the safety endpoints up to Week12, which will be performed after all subjects complete the 12-week assessments and all data are cleaned.

[REDACTED]

[REDACTED] For data that are collected on an ongoing basis throughout the study (eg adverse events, concomitant medications), the subject's actual Week 12 visit date will be used as a cutoff for the data in the primary analysis. For subjects who did not complete Week 12 and withdrew early, the cutoff for the data would be the earliest of the subject's projected Day 85 and discontinuation date.

- Full analysis:  
After the subjects in the OL safety extension portion of the study complete the study up to Week 24, the database will be locked, and the corresponding analysis tables produced for the primary analysis will be updated with the descriptive statistics of the Week 16, Week 20, and Week 24 data added.

Thus, exactly the same set of outputs will be produced for the primary analysis and full analysis.

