Hematology: Hemoglobin, hematocrit, red blood cell count, WBC count (with differential [lymphocytes, neutrophils, eosinophils, basophils, and monocytes]), and platelet count.

Blood Chemistry: albumin, alkaline phosphatase, AST, ALT, direct bilirubin, total bilirubin, blood urea nitrogen, calcium, chloride, creatine kinase (Screening only), creatinine, gamma-glutamyl transferase, glucose, lactate dehydrogenase, potassium, sodium, and uric acid.

Other tests: HbA1c, HIV, hepatitis B, and hepatitis C at Screening. Coagulation tests at Screening: activated PTT, PT, and INR. Coagulation tests may be repeated prior to the index and repeat injection, if deemed necessary by the Investigator.

Urinalysis: Dipstick analysis: color, turbidity, specific gravity, pH, glucose, protein, ketones, urobilinogen, bilirubin, blood nitrate, leukocyte esterase, and microscopic examination when indicated by dipstick results.

Urine drug screen: Includes opiates, barbiturates, benzodiazepines, tricyclic antidepressants, cannabinoids, PCP, cocaine, ecstasy, and amphetamines. A urine drug screen will be obtained at Screening, Baseline (D1), W2, and W4. A urine drug screen may be repeated if deemed necessary by the Investigator.

For females of childbearing potential: Serum pregnancy test at Screening. Urine pregnancy test at Baseline (D1) and at Repeat Injection. A urine pregnancy test may be repeated if deemed necessary by the Investigator.

Laboratory samples will be analyzed by a central laboratory [REDACTED] to ensure consistent interpretation of results. Samples are to be shipped to [REDACTED], [REDACTED]. In the event of an unexplained clinically noteworthy abnormal laboratory test value, the test should be repeated immediately and followed up until it has returned to the normal range and/or an adequate explanation of the abnormality is found.

3.5.7.6 Adverse Events:

All AEs occurring after the subject signs the ICF through W24, D169 will be recorded. See [Section 4](#) for additional information.

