4.2 Reporting Procedures and Requirements

4.2.1 Adverse Events

AEs occurring after the subject signs the ICF until the 30 days after the last study visit will be recorded. Any AEs occurring before the start of treatment (ie, before the first dose of the IP) will be recorded in the medical history. Also, the sign, symptom, or disease present before starting the treatment period are only considered AEs if they worsen after starting the treatment period.

If a subject has new or worsening pain, or onset of new neurological symptoms, a follow-up MRI may be obtained after consultation with the Medical Monitor.

If the investigator detects an AE in a study subject within 30 days after the last scheduled follow-up visit and considers the event possibly related or related to prior study treatment, the investigator should report it to the sponsor [REDACTED]

The investigator should report all AEs on the AE page(s) of the eCRF and source documents (if the eCRF is unavailable for direct data entry [DDE]), regardless of seriousness, severity, and causality. Whenever possible, an AE will be reported using a diagnostic term, (eg, “common cold” or “upper respiratory infection” rather than “runny nose, cough, mild fever”) and should be described with the attributes described in [Section 4.1.5](#).

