4.2.3 Serious Adverse Events

Each AE will be assessed to determine whether it meets seriousness criteria ([Section 4.1.2](#)). If the AE is considered serious, the investigator should report this event to [REDACTED] as outlined below and also to the IRB/IEC according to its standard operating procedures.

If the investigator detects an SAE in a study subject within 30 days after the last scheduled study visit, and considers the SAE related or possibly related to prior study treatment, the investigator should report it to sponsor [REDACTED]

The investigator should report all SAEs to [REDACTED] on the eCRF within 24 hours of the Investigator, designee or site staff’s knowledge of the event regardless of relationship to study drug.

If the site experiences a temporary disruption of the eCRF system, a back-up paper SAE Report Form will be available for site staff to complete.

- Site staff will complete the paper SAE report form and email it within 24 hours to the following address [REDACTED]
- Only in cases where the email system is unavailable, site staff will send the SAE by fax to: [REDACTED]

█ [REDACTED]
█ [REDACTED]
█ [REDACTED]

All recorded SAEs, regardless of relationship to study treatment, will be followed up until resolution, stabilization, or the subject is lost to follow-up and cannot be contacted. In circumstances where the Investigator is unable to contact the subject, the Investigator must provide a written statement to [REDACTED] confirming that the subject is lost to follow-up. SAEs that are ongoing at V5 (D29) should be followed until resolved.

Additional follow-up information must be reported in the eCRF within 24 hours of awareness following Investigator (or site) awareness of the information. The Investigator should not delay reporting an SAE to obtain additional information. Additional information, when available, should be reported to [REDACTED] by the reporting procedures described above.

The sponsor or its representative will be responsible for determining and in turn, reporting SAEs to regulatory authorities per the applicable regulatory requirements.

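### In the Week 12 reporting cut, adverse events in early withdrawers stop at the discontinuation date although Protocol 4.2.1 collects them for longer, and the protocol gives conflicting ends for adverse event collection

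*SAP*

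**What the plan says.** SAP 7.1 sets the cutoff for data collected continuously, and gives adverse events and concomitant medications as its examples. For subjects who reach Week 12, "the subject's actual Week 12 visit date will be used as a cutoff for the data in the primary analysis". For those who did not complete Week 12 and withdrew early, it is "the earliest of the subject's projected Day 85 and discontinuation date". Both rules are stated for the primary analysis, run once all subjects have finished the 12-week assessments. The full analysis after Week 24 repeats the outputs, and no adverse event cutoff is given for it.

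The protocol describes the end of adverse event collection in several ways:

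- Section 3.5.7.6: "All AEs occurring after the subject signs the ICF through W24, D169 will be recorded".
- Section 4.2.1, first paragraph: "AEs occurring after the subject signs the ICF until the 30 days after the last study visit will be recorded".
- Section 4.2.1, third paragraph: reporting to the sponsor applies to an event detected "within 30 days after the last scheduled follow-up visit and considers the event possibly related or related to prior study treatment".
- Section 4.2.3 has a parallel paragraph for SAEs, opening "If the investigator detects an SAE in a study subject within 30 days after the last scheduled study visit" and again limited to events judged at least possibly related.

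SAP 7.2.2 defines the Safety Analysis Population as all randomized subjects who received the index injection, and SAP 7.13 uses it for every safety analysis. SAP 7.13.1 defines a treatment-emergent event by its onset alone, with no closing date, and asks for summaries through 12 weeks covering events, SAEs, withdrawals and deaths.

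**The concern.** The index treatment is a single injection, so leaving the study does not end exposure: a subject who leaves on Day 20 has had the same index dose as one who stays. An SAE on Day 30 in that subject falls within 12 weeks of dosing and within the first-paragraph window of Protocol 4.2.1. It is still past the SAP cutoff for the Week 12 tables.

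The effect has one direction. Early leavers count in the denominator, but their later events cannot enter the numerator, so incidence through 12 weeks can only be understated relative to what was collected. If withdrawal is related to adverse events or differs between arms, so will the understatement. This is also the first planned unblinded look at aggregate safety: neither an interim analysis nor any data safety monitoring board analysis is planned (SAP 8 and 9).

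The conflicting protocol windows are a separate problem. Sites that follow different sections will observe subjects for different lengths of time. This matters most after a late repeat injection, where scheduled follow-up is shortest.

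**Working it through.** The plan states no figure to reproduce here, and the sample size text is redacted. The check is day arithmetic.

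**Inputs.** Early-withdrawer cutoff: SAP 7.1. Collection to the last study visit plus 30 days: Protocol 4.2.1, first paragraph. Day 85 = Week 12, Day 141 = Week 20, Day 169 = Week 24: Protocol 3.1. About 400 randomized and a goal of 332 completing Week 4: protocol synopsis. Assumption: the last study visit falls on the discontinuation date, day *d*.

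**Days collected but not tabulated.**

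SAP cutoff = min(85, *d*). Collection end = *d* + 30. Days lost before Day 85 = min(85, *d* + 30) − min(85, *d*).

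| *d* | SAP cutoff | Collection end (4.2.1) | Days lost before Day 85 |
|---|---|---|---|
| 15 | 15 | 45 | 30 |
| 29 | 29 | 59 | 30 |
| 55 | 55 | 85 | 30 |
| 57 | 57 | 87 | 28 |
| 71 | 71 | 101 | 14 |
| 84 | 84 | 114 | 1 |
| 85 | 85 | 115 | 0 |

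The loss is the full 30 days up to Day 55, and 85 − *d* days after that.

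**Ceiling on person-time.** Planned 12-week person-time is 400 × 84 = 33,600 days. The number of early withdrawers cannot be read from the documents, so a range is assumed, with every withdrawal by Day 55:

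- 20 withdrawers: 20 × 30 = 600 days; 600 / 33,600 = 1.8%.
- 40 withdrawers: 40 × 30 = 1,200 days; 1,200 / 33,600 = 3.6%.
- 68 withdrawers: 68 × 30 = 2,040 days; 2,040 / 33,600 = 6.1%.

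The top value is 400 − 332 = 68 (17% of 400), the planned shortfall at Week 4, taken as if all of it were early withdrawal.

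**Protocol windows compared.** For a completer, 3.5.7.6 ends collection at Day 169, and the first paragraph of 4.2.1 ends it at 169 + 30 = Day 199. After a repeat injection on Day 141, follow-up for all adverse events is 169 − 141 = 28 days under the former and 28 + 30 = 58 days under the latter. Under the third paragraph of 4.2.1, the last 30 days bring only related or possibly related events to the sponsor. Its anchor is also different: the last scheduled follow-up visit instead of the last study visit.

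**The case against.** A pre-stated cutoff for each subject is a normal feature of a reporting cut and not an error in itself. The cutoff is also confined to the Week 12 cut. A reader might infer that these events vanish from the safety reporting altogether, and the documents do not support that: the full analysis states no adverse event cutoff, the treatment-emergent definition has no end date, and SAP 7.13.1 lists all adverse events. Nor does either document call the Week 12 analysis the main safety report.

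The premise of 30 more days for all events is itself contestable. One workable reading of the protocol is all events to the end of the study, then related events only for 30 days. Section 3.5.7.6 also refers the reader to Section 4. This weakens any claim that the SAP plainly discards data that the protocol plainly requires. It does not remove the conflict, because the first paragraph of 4.2.1 has no such restriction.

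Two further inferences go too far. It is tempting to say that 3.5.7.6 keeps a Day 20 withdrawer under observation to Day 169. Protocol 3.5.5, however, performs the Week 24 procedures at early termination, so collection can be read as ending there. It is also tempting to add events that come to light at a termination visit held after discontinuation, but no readable text defines the discontinuation date or separates it from that visit.

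The 6.1% is calendar time, not lost events. Some of the 68 may have been randomized but never dosed, and so fall outside the Safety Population, or may simply have missed Week 4. Subjects who withdraw consent or are lost to follow-up may supply little afterwards.

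Finally, parts of SAP 7.1, one item in SAP 11 and the table list are redacted and may hold further detail. In the readable text nothing repairs the gap: the last-visit censoring rule in SAP 7.3.3 is for time-to-event analyses.

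**Conclusion.** The concern holds for the Week 12 reporting cut. Under the first paragraph of Protocol 4.2.1, events collected in early withdrawers between discontinuation and Day 85 are left out of the 12-week tables, while those subjects remain in the denominator. The size is at most 30 days per withdrawer, and 1.8% to 6.1% of planned person-time for an assumed 20 to 68 withdrawers. This is a ceiling. It rests on the last visit coinciding with discontinuation, on all withdrawals occurring by Day 55, and on the broad reading of 4.2.1. The number of events affected cannot be estimated from the documents. Permanent exclusion from the final report is not shown.

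The conflict over when collection ends stands independently of the SAP cutoff: Day 169 against Day 199 for completers, 28 against 58 days after a Week 20 repeat injection, and all events against related events only within 4.2.1 itself. Both matters are modest in size and should be corrected, because the understatement runs one way and the remedy is cheap.

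**What to change.** In SAP 7.1, for adverse events in subjects who withdrew before Week 12, set the Week 12 cutoff to the earlier of projected Day 85 and the end of the protocol's adverse event collection window, which is 30 days after the last study visit under the first paragraph of 4.2.1. Keep the discontinuation date for concomitant medications. State the adverse event window for these subjects in the full analysis too.

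Reconcile Protocol 3.5.7.6, both paragraphs of 4.2.1, and 4.2.3 to one collection end, with one anchor visit and one scope (all events or related events only). Apply it alike to completers, early withdrawers and subjects with late repeat injections. Replacing the text of 3.5.7.6 with a pointer to 4.2.1 would not be enough, since 4.2.1 has two anchors and two scopes.

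The cost is one SAP sentence and a protocol wording correction. No data are needed beyond what the first paragraph of 4.2.1 already asks for, although sites that followed a narrower reading may not hold all of it. Adverse event counts in the Week 12 tables may rise slightly.

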## 7.2 Analysis Population

### 7.2.1 Screened Population

This consists of subjects that signed the informed consent form and were assigned a user subject number.

### 7.2.2 Safety Analysis Population

This is defined as all randomized subjects who received an index injection (study drug). For safety analyses, subjects will be grouped based upon the treatment received (even if different from what they were randomized to).

### 7.2.3 Modified Intent-to-Treat (mITT) Population

This will be the primary population for efficacy analyses and will include all subjects who were randomized and received drug delivery injection (for index injection only) in correct anatomic location.

[REDACTED]

## 7.2.4 Per Protocol Population

This will include all subjects in the mITT population who do not have a major protocol deviation. Major protocol deviations will be reviewed and determined prior to unblinding. The Per Protocol (PP) population will be determined prior to treatment unblinding and will be used for supportive sensitivity analyses.

Subjects excluded from the analysis populations and the reason for their exclusion will be listed in Appendix 16.2.

## 7.2.5 Completed Subject

For the purposes of analysis, there are 3 types of completers in this trial:

- A Primary Efficacy Endpoint Completer is defined as one who receives an index injection and who has enough data to calculate data for the primary analysis period (i.e. first four weeks) regardless if Week 4 visit was completed.

- A 12-week Completer is defined as one who receives an index injection and completes the study through Week 12.
- A 24-week Completer is defined as one who receives an index injection and completes the study through Week 24.

A subject does not necessarily have to complete all visits up to Week 12, or Week 24 to be considered as a 12-week Completer or 24-week Completer respectively. As long as the Week 12 or Week 24 visits are completed, the subject will be considered as a 12-week Completer or 24-week Completer respectively.

### 7.3 Derived Data

This section describes the derivations required for statistical analysis. Unless otherwise stated, variables derived in the source data will not be re-calculated.

#### 7.3.1 Race

If more than one race category has been selected for a subject, these race categories will be combined into a single category labeled “Multiple Race” in the summary tables. The listings will reflect the original selected categories.

#### 7.3.2 Baseline

Except otherwise specified, baseline is defined as the last non-missing value (either scheduled, unscheduled or repeat) before the subject receives the first dose of SP-102 TF or placebo injection on D1. Baseline calculations for variables collected in the diary are described in the efficacy analyses section.

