3.4 Treatments

3.4.1 Details of Study Treatments

Information about the IPs is provided in [Table 3.1](#).

Table 3.1: Details of Investigational Products

	SP-102	Placebo
Ingredient	[REDACTED]	
Manufacturer	[REDACTED]	
Dose(s)	[REDACTED]	
Route	[REDACTED]	
Formulation	[REDACTED]	
Strength(s)	[REDACTED]	

SP-102 drug product is comprised of [REDACTED]

The drug product is a sterile [REDACTED]

[REDACTED] which is intended to be delivered via a TF injection, using 6-inch long extension tubing. The placebo, [REDACTED]

[REDACTED]. While the drug is sterile manufactured and is sterile for injection, the outside of the syringes is not sterile; thus, attachment of the syringe and IP injection should be the last step prior to removal of needle and finishing the procedure.

Under Good Manufacturing Practices, SP-102 was manufactured by [REDACTED]. All IP will be kept in a locked area with limited access. [REDACTED]

[REDACTED] Deviations of storage temperature outside this range should be documented and Semnur or designee should be promptly notified. IP kits should not be frozen. If any component of the IP kit is damaged, Semnur or designee must be notified as soon as possible.

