3.5.7 Safety Assessments

3.5.7.1 Physical Examination:

A complete physical examination, including examination of general appearance, skin, neck, eyes, ears, nose, throat, heart, lungs, abdomen, lymph nodes, extremities, and musculoskeletal system, will be performed at Screening. Specific musculoskeletal examination focusing on lumbar spine and lower extremities to exclude musculoskeletal sources of the predominant pain, such as SI joints and trigger points, will be performed in standardized manner and recorded. Height (in inches without shoes) and weight (in pounds) will be recorded at Screening.

3.5.7.2 General Neurological and Targeted Neurological Examinations:

A general neurological examination will include evaluation of mental status (awareness of person, place, and time), cranial nerves, motor function and balance, sensory exam (ability to feel) and reflexes. A targeted neurological examination demonstrating findings of, focusing on signs and symptoms of lumbosacral radiculopathy, including straight leg raise test, will be performed according to the checklist (see [Appendix A](#)). Both general and targeted neurological exams are to be performed by the same trained clinician throughout the study, if possible. Training for conducting examination will be available on video. General and targeted neurological examinations will be performed at Screening, Baseline (D1), W2, W4, W12, and W24, as well as if the repeat injection is administered.

The blinded Investigator will summarize and document the MRI findings based on the Lumbar Disc Nomenclature, the clinical presentation, and the Injection Plan in the eCRF prior to Baseline (D1).

3.5.7.3 Vital Signs and Body Weight:

Vital signs will include systolic and diastolic BP and heart rate. During the usual clinic visits, the subject is to be seated for approximately 3 mins before vital signs are recorded. During the injection procedure, the vital signs will need to be collected while the subject is in prone position on the fluoroscopy table ([Appendix D](#)). Vital signs will be recorded at each clinic visit.

3.5.7.4 Electrocardiogram:

Standard 12-lead ECGs will be measured on the site machines at Screening. The ECG results will be documented in the eCRF.

3.5.7.5 Laboratory Parameters:

The following clinical laboratory tests are to be performed at Screening and W24 unless noted below:

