### 7.13.3 Vital Signs

Descriptive statistics for observed values and changes from baseline in the following vital signs will be presented by treatment group, visit, and timepoint within visit:

- Systolic blood pressure (mmHg)
- Diastolic blood pressure (mmHg)
- Pulse rate (Heart Rate) [bpm]

Vital signs data will be summarized separately for both the primary and the secondary analysis periods. Vital sign values will be categorized into the following potential clinical concern categories if applicable, and then summarized.

[figure not shown]
Vital Sign	Potential Clinical Concern Categories
Systolic blood pressure	$\geq 160$ mmHg
Diastolic blood pressure	$\geq 100$ mmHg
Pulse rate (Heart Rate)	$< 60$ or $> 100$ bpm

All vital sign measurements including the position of the subject when the measurement was taken will be listed.

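### The vital-sign baseline takes no account of position, so change from baseline mixes seated and prone readings whichever Day 1 reading is used

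*SAP*

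**What the plan says.** SAP 7.3.2 gives one general rule: "baseline is defined as the last non-missing value (either scheduled, unscheduled or repeat) before the subject receives the first dose". It opens with "Except otherwise specified", so a variable can have its own definition. The SAP uses that freedom for the diary pain scores (for example 7.12.6.5 for worst pain), but the readable text of SAP 7.13.3 has no such definition for vital signs.

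Protocol 3.5.7.3 uses two positions. For ordinary visits: "During the usual clinic visits, the subject is to be seated for approximately 3 mins before vital signs are recorded". For the injection: "During the injection procedure, the vital signs will need to be collected while the subject is in prone position on the fluoroscopy table", with a reference to Appendix D.

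SAP 7.13.3 describes observed values and changes from baseline by arm, by visit and by time of reading inside a visit. Position appears only in a listing: "All vital sign measurements including the position of the subject when the measurement was taken will be listed". SAP 7.3.8 drops unscheduled post-baseline readings but makes an exception for repeat-injection visits, whose assessments are all analysed. SAP 7.4 asks for 95% limits around each arm's mean change. Change from the Day 1 baseline in vital signs is a listed safety endpoint (SAP 4.4; Protocol 5.2.9).

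**The concern.** A change from baseline can be interpreted only if both readings were taken under comparable conditions. The protocol prescribes a rested, seated reading for one setting and a prone reading during an invasive procedure for the other. The baseline rule chooses by time alone, so posture and procedural conditions can enter the subtraction.

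At stake are the mean changes in systolic pressure, diastolic pressure and heart rate in each arm, with their confidence limits. A shift that belongs to the measurement would be read as a change over time. Since its direction is unknown, it could hide a real rise or produce an apparent one.

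**Working it through.** The readable text gives no planned figure for vital signs, so there is nothing to reproduce. The check is a comparison of the rules, followed by simple algebra.

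**Inputs**
- Baseline rule: last pre-dose value, any position (SAP 7.3.2).
- Position: seated at usual visits, prone during the procedure (Protocol 3.5.7.3).
- Repeat-injection readings: all analysed (SAP 7.3.8).
- Timing of on-table readings relative to dosing: not visible. The schedule of assessments (Table 3.2) and the Baseline Visit procedures (Protocol 3.5.2.3) are redacted, and Appendix D is not in the public text.
- Sample size: about 400 randomised 1:1 (Protocol synopsis), so 400 / 2 = 200 per arm.
- Assumptions, not in the documents: the shift d, and an SD of change in systolic pressure of 12 mmHg.

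**Notation.** Let S0 be an arm's mean seated pre-dose value, St its mean seated value at time t, and d the mean seated-minus-prone difference, including any effect of the procedure. A prone reading then averages S - d.

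**Case A: the last pre-dose reading is prone.** Baseline is S0 - d.
- Seated clinic visit: St - (S0 - d) = (St - S0) + d.
- Prone reading at the repeat injection: (St - d) - (S0 - d) = St - S0, so no shift if d is the same at both procedures.

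**Case B: the last pre-dose reading is seated.** Baseline is S0.
- Seated clinic visit: St - S0, no shift.
- Prone reading after dosing or at the repeat injection: (St - d) - S0 = (St - S0) - d.

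| Assumed d (mmHg) | Case A, seated visits | Case B, prone readings |
|---|---|---|
| -10 | -10 | +10 |
| -5 | -5 | +5 |
| 0 | 0 | 0 |
| +5 | +5 | -5 |
| +10 | +10 | -10 |

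The cases are alternatives for a given subject. If only a share p of an arm has a prone baseline, the shift in that arm's seated-visit mean is p x d.

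**Between arms.** In Case A the SP-102 minus placebo difference in change is the true difference plus (d in SP-102 - d in placebo). This extra term is 0 if the two shifts are equal.

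**Scale, under the assumed SD.** The 95% half-width for one arm's mean change is 1.96 x 12 / sqrt(200) = 1.66 mmHg. A shift of 3, 5 or 10 mmHg in either direction would be 3/1.66 = 1.8, 5/1.66 = 3.0 or 10/1.66 = 6.0 times that, and a shift of 0 would do no harm. The limits reflect sampling error only, so they do not widen to cover d.

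**The case against.** A reader might infer that the baseline actually is the prone on-table reading, because the protocol says of the syringe that "attachment of the syringe and IP injection should be the last step prior to removal of needle and finishing the procedure", which places most of the procedure before dosing. The documents do not support that step. The sentence is there because the outside of the syringe is not sterile, and it says nothing about when vital signs are taken. A reading during or just after delivery, with the subject still on the table, fits Protocol 3.5.7.3 equally well. A prone pre-dose reading is plausible but not established. It also cannot be argued that clinic visits and repeat-injection readings are both mismatched on account of posture: the algebra shows one or the other.

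Other points against the concern:
- **Separate rows by time of reading.** This can keep prone and seated post-baseline values apart. It does not change which baseline is subtracted from each row.
- **Clinical-concern categories.** They use absolute values, so the baseline rule does not affect them. They carry no position restriction, however.
- **Randomisation.** An equal shift cancels between arms. This stands, but equality is an assumption: the injections are transforaminal and intramuscular, and Protocol 3.1 says the control was chosen partly to spare placebo subjects procedural risk. In the four-group tables, only the two groups given a repeat injection have readings from that visit.
- **Assumed magnitude.** This stands in full. The documents fix neither the size nor the sign of d, and zero is possible.

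**Conclusion.** The point holds as a conditional one. The baseline rule ignores position, two positions are in use, and no exception for vital signs is visible. Whichever reading comes last before dosing, some of the tabulated changes compare prone with seated: the clinic visits if it is prone, the on-table or repeat-injection readings if it is seated.

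The effect is confined to descriptive within-arm changes and their 95% limits, by d or -d, of unknown size and sign. The randomised contrast is largely unaffected if the shift is similar in both arms. The conclusion assumes that the redacted pages and Appendix D contain no vital-sign baseline rule. If they do, SAP 7.13.3 need only cite it. The change is worth making because the endpoint is a stated safety endpoint and the remedy is cheap, but the point does not threaten the trial's main conclusions.

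**What to change.** In SAP 7.13.3:
1. Define the vital-sign baseline for clinic-visit changes as the last seated value before the index injection, taken on Day 1 or, if there is none, at Screening.
2. Tabulate change from baseline at clinic visits from seated values only.
3. Summarise prone on-table readings, at the index and repeat injections, in a separate table by time of reading. Show change against a prone pre-dose reading from the same procedure where one exists, and observed values alone where none does.

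The position field already planned for the listing supplies the filter, so trial conduct does not change. The cost is a short SAP edit, a position filter and one small extra table. The drawback is that some subjects may have no seated Day 1 value, and their baseline would then be the Screening reading, taken up to about three weeks earlier. The number of such subjects should be reported.
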